Assignment to either intervention will occur before levelling and alignment stage.

D] Blinding:

Blinding of the operators: Blinding will not be possible for the operators during the application interventions and during the follow up visits. The principal operator is responsible for assigning subjects to interventions according to the concealed allocation, appliance activation at follow up visits, dental impressions and acquisition of dental casts.

Blinding of the outcome assessors: It is a single blinded study, therefore, only the outcome assessors will be blind. The patients name will be sealed from pre and

post radiographs and study models. Then two assessors will carry out, blindly and independently, the measurements and analysis of the study.

III) Data collection, management and analysis:

A] Data collection methods:

Primary outcomes:

1. Total Retraction Duration: to assess the timing of antero-posterior movement of anterior teeth and first molars, the principle investigator will take study models for every participant monthly during the follow up visits. Then will digitize the models and identify the landmarks, reference lines and planes on the pre, interim and post-retraction digital dental models for measurements reading. Also, by identifying the landmarks, reference lines and planes using CBCT taken before and after the completion of retraction.

Secondary outcome:

1. Anchorage loss: will be accessed by the principal investigator via CBCT taken before and after the completion of retraction by identifying the landmarks, reference lines and planes, then will interpret the measurements in degrees and millimeters.

2. Pain: Each patient will fill a questionnaire regarding his treatment experience in a VAS scoring from 1-10. The questionnaire will include several questions related to oral hygiene, pain and discomfort experienced throughout the trial.

B] Data management:

A colleague outside the research team will enter the data and organize it in excel sheets in the computer of the orthodontic department.

Data will include all photographs, models, radiographs and filled questionnaire.

C] Statistical Analysis:

- The principle investigator will be responsible for the extraction of the required data from the CBCT taken before and after retraction as well as the study models taken at every follow up visit. The data will be sent to a specialized statistician.

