- The specialized statistician will be responsible for the statistical analysis of the study by:
 1. Presenting the data as mean, standard deviation (SD) and Standard error (SE) values.
 2. Using Paired t-test to compare between the friction and the frictionless group of retraction as well as to compare between the pre-and post -treatment data for each group.
 3. Using Anova test to determine the rate of anterior segment retraction.
 4. Statistically evaluate the patient acceptance for both techniques.
- For this study, the specialized statistician will use IBM11 SPSS12 Statistics Version 20 for Windows to perform the required statistics.
- The significance level will be $P \leq 0.05$. Highly significant variables are detected when P value is less than 0.01.

Assessors Reliability:

- To achieve high reliability for measurements, the supervisor will choose a well-experienced inter-examiner during the study.
- A training session will be provided for the examiners to ensure standard measurements techniques.
- Each examiner will complete the measurements on a model and will repeat the procedure after one week to assess the intra- and inter-examiner reliability.
- The supervisor will compare the measurements of the two assessors for disagreement with a difference of more than one millimeter.
- The supervisor will evaluate the amount of variation in measurements among and between examiners to test the performance of each assessor.
- The examiner with less reliability will receive additional training but will be replaced during the study.
- The specialized statistician will calibrate the intra and inter-examiner reliability for the measurements of the study by the Intra-class correlation coefficient (ICC). The closer the ICC to 1.0, the higher reliability between assessors. According to Fleiss:" ICC values between 0.7 and 0.9 represent good reliability." The kappa scores between study examiners will be calculated, a range of 0.60-0.80 will represent acceptable reliability.

IV) Method Monitoring:

A] Data Monitoring: An independent Data Monitoring Committee (DMC) will monitor the results of the study. The Committee will include the trial's supervisors, who will periodically review the trial data and identify the need for any adjustments or modifications during the study.

B] Interim Analysis: no interim analysis will be performed during the study.

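### The statistician is outside the stated blind and no arm-masked data file is planned, while exclusions and the between-arm test are left open

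*Combined protocol and SAP*

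**What the plan says.** Section II) D] Blinding states "It is a single blinded study, therefore, only the outcome assessors will be blind". It then says that patient names are hidden on radiographs and models, and continues: "Then two assessors will carry out, blindly and independently, the measurements and analysis of the study".

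Section III) C] Statistical Analysis has the principal investigator extract the data, after which "The data will be sent to a specialized statistician". It gives the statistical work to that separate person: "The specialized statistician will be responsible for the statistical analysis of the study by" a short list of methods. The list includes "Using Paired t-test to compare between the friction and the frictionless group of retraction" and "Statistically evaluate the patient acceptance for both techniques". It defines no analysis set.

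Two arrangements that could support masking already exist. Under III) B] Data management, "A colleague outside the research team will enter the data and organize it in excel sheets". Under V) D] Confidentiality, records carry a coded ID, for the stated purpose of protecting participants' identity. Neither is said to hide the arm, and section II) A] Sequence generation openly defines group A as en-masse and group B as two steps.

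**The concern.** The statistician has real decisions to make. The between-arm test is paired and is named for friction versus frictionless groups. Both arms here use friction, and the design is two independent parallel groups, so the test cannot be run as written and a replacement must be chosen. Patient acceptance has no method. The list of criteria for discontinuing or modifying treatment ends with non-compliant patients and does not say how they are analysed. The sample size section allows for a fall from 15 to 10 per group, so a few exclusions would not look unusual.

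The protocol's rationale says that en-masse is expected to be the better option, so a direction of preference is on record. If exclusions are decided with the arms in view, they can be made, even without intent, in that direction. The type I error for a claim that en-masse is faster would then exceed its nominal level, and a reader of the report could not tell.

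**Working it through.** **The plan's own figure.** The sample size section gives SD 0.76, difference 1.0, power 0.8 and alpha 0.05 (taken as two-sided). The normal approximation is n = 2 × (1.96 + 0.84)² × 0.76² / 1.0² ≈ 9.1, rounded up to 10 per group, as stated. Exact t-test power is 0.795 at 10 per group and 0.935 at 15. This point disputes none of these figures, and masking changes none of them.

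**Who is blind, from the text.**
- The blinding section restricts blinding to the outcome assessors.
- The statistical section gives the analysis to a statistician, a different role.
- The statistician is therefore outside the stated blind.
- No section says whether the file sent carries arm labels, codes or neither.

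**What masking can and cannot change.** The simulation assumes no difference between arms, 15 patients per arm, and normal durations with mean 8 and SD 1.5 months. The mean and SD are assumptions, because the documents give no distribution of duration in months. They affect only the log-scale test, since the ordinary t statistic does not depend on location or scale. Tests are two-sided at 0.05. A false claim for en-masse is a significant result with the shorter mean in that arm.

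1. *One fixed t-test on all patients.* The nominal rate is 5% in total, so 5% / 2 = 2.5% in favour of en-masse.
2. *Smallest p-value of four analyses* (t-test, rank test, t-test on logs, t-test with two patients per arm left out). The total is about 7.3% (6.8% to 7.9% across repeat runs). False claims for en-masse are about 3.8%, whether the analyst knows the arms or sees only codes. By symmetry they should be about half the total, and 7.3% / 2 ≈ 3.7%.
3. *Independent t, paired t and rank test only.* The smallest p-value gives 6.6%, against 4.8% for the fixed t-test in the same run. Coding leaves this unchanged too.
4. *Leaving out only the slowest en-masse patient,* then an ordinary t-test of 14 against 15. False claims for en-masse are about 5.7% (5.3% to 6.0% across repeat runs), and 5.7 / 2.5 ≈ 2.3 times nominal.
5. *Leaving out only the two slowest en-masse patients,* 13 against 15. False claims for en-masse are about 10.1% (9.4% to 10.2% across repeat runs), and 10.1 / 2.5 ≈ 4 times nominal.

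Lines 2 and 3 measure the effect of not fixing the test. Lines 4 and 5 require knowing which arm is en-masse, and only these describe something masking takes away.

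**The case against.** Two stronger readings are tempting, and neither is supported.

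A reader might infer that the statistician will certainly work with the arms visible. The documents do not say that. They are silent on what the file contains, records carry coded IDs, and the sentence after the blinding statement speaks of blind analysis. That sentence concerns the two assessors, and the statistical analysis is assigned elsewhere, so it leaves the matter unclear and does not settle it.

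A reader might also infer that a coded file would remove the false-positive inflation from choosing among tests. It would not. A masked analyst who picks the smallest p-value has the same 7.3%. Naming one test in advance cures that. Nor is the list a fully open menu: a t-test, ANOVA, software and significance level are named, though mis-specified, and log transformation appears nowhere in the plan.

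It can fairly be added that a masked statistician is a refinement many small trials omit, and that an analysis set fixed in advance would itself close most of the room for directed exclusions. Both are true. Masking still protects the judgements that remain, such as data queries and the handling of patients who do not complete space closure.

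Masking the statistician also leaves a separate conflict untouched: the data collection section has the unblinded principal investigator identify landmarks and assess anchorage loss, although assessors are said to be blind.

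**Conclusion.** The point holds as a minor, worthwhile improvement. The stated blind excludes the statistician and no arm-masked file is planned. Because the analysis set is open and the named between-arm test does not fit the trial, that person must decide on exclusions and a test, possibly knowing the arms.

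What masking prevents is decisions directed at one arm. The illustration is a rise in false claims for en-masse from 2.5% to about 5.7% or 10.1% when only its one or two slowest patients are left out. This is a worst case, not a forecast, and nothing in the documents suggests that anyone intends it. It assumes normal durations, 15 per arm and no true difference.

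**What to change.** In II) D] Blinding, state that the outcome assessors and the statistician are blind to allocation. Have the data-entry colleague outside the team send the file with neutral arm codes other than the protocol's A and B, and without stage or force fields, which differ by arm and would reveal it. Someone other than the statistician should hold the key until the analysis is locked.

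In III) C] Statistical Analysis, before any outcome data are seen, name one independent-groups test for en-masse versus two-step duration and define the analysis set as all randomised patients. This part controls the inflation from choosing among tests. Coding alone does not.

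The cost is a little extra data handling; sample size and power are unchanged. Masking may be imperfect if the pattern of the data reveals the arm, and the report should say so.

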
Rationale for carrying out the trial:

In order to achieve patient satisfaction and shortest treatment duration, there is no gold standard guidelines which technique achieves the most efficient results at the shortest period of time of retraction. The first premolars are usually the main choice of extraction in bimaxillary protrusion cases, maximum anchorage of the posterior teeth become of great importance for two reasons; first to retract the anterior teeth to their greatest extent and second to increase the chances of correcting the profile maximum retraction of anterior teeth into the extraction space and retraction is the ideal treatment choice. (2,3)

Space closure can be achieved by two methods either the two-steps (4) or by en-masse technique. A debate was raised between the two methods regarding friction mechanics.

It has been recommended that two steps techniques would provide less load on the posterior teeth thus minimal anchorage loss but on the other hand, separate canine retraction followed by incisors retraction would take longer time than closing it in a single step and it is aesthetically unacceptable (5) for some patient as there is a space after canine retraction and it persists up until the full retraction of anterior segment, for these reasons en-masse retraction is expected to be superior treatment option as retraction will be done by one step (6).

Nowadays, Orthodontists prefer using the en-masse technique because of its simplicity and the extraction space will be closed in one step so better aesthetics. But theoretically this technique may provide more loads on posterior segment so more risk of anchorage loss.

In general orthodontic treatment takes long time especially in extraction cases by average two years treatment time (7). So the longer treatment duration, the greater risks on the dentition by a way of root resorption (8), periodontal disease and enamel decalcifications (9). Thus, reduction of the treatment duration is of prime concern to both the patient as well as the orthodontist.

For many years, practitioners have been looking for an efficient force system that can close extraction spaces quickly, aesthetically, accurately, and effectively. It was determined that both were effective methods for retraction (10). However, there is no evidence which technique offers shorter treatment duration with best retraction and space closure.

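### Sealing the patient's name does not mask the arm on the two-step pre-intervention cast or on interim two-step casts, so the assessor-blinding claim holds at most for records that do not show the canine space

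*Combined protocol and SAP*

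**What the plan says.** Section II) D] Blinding states: "It is a single blinded study, therefore, only the outcome assessors will be blind". The masking step follows: "The patients name will be sealed from pre and" post radiographs and study models. It continues: "Then two assessors will carry out, blindly and independently, the measurements and analysis of the study". No section describes cropping, hiding part of the arch, removing visit dates or shuffling the files.

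Section III) A] Data collection methods has models made at every visit: "the principle investigator will take study models for every participant monthly during the follow up visits". The same person is then to digitise them and "identify the landmarks, reference lines and planes on the pre, interim and post-retraction digital dental models for measurements reading".

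The Rationale describes how the techniques differ. In two-step treatment, "separate canine retraction followed by incisors retraction would take longer time than closing it in a single step", and for some patients the appearance is unacceptable because "there is a space after canine retraction and it persists up until the full retraction of anterior segment". For en-masse, "the extraction space will be closed in one step so better aesthetics".

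The Clinical Procedure (section I) C]) takes pre-intervention records in the en-masse arm after alignment and immediately before retraction. In the two-step arm it takes them once the canines have been retracted. Section I) D] Outcomes defines T0 as the start of retraction and T1 as complete space closure. Section I) E] Participant timeline lists T0 records for every participant before retraction.

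**The concern.** Covering a name works only if nothing else on the record identifies the group. Here the treatment changes the shape of the arch in a way the protocol calls visible and, for some patients, unsightly. A trained assessor who sees that space on a cast can infer the arm.

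What is at stake is the trial's only blinding. Landmark placement on digital models calls for judgement, and a reader who knows the arm may place landmarks or read residual space differently. The planned checks between examiners would not reveal this: intra-class correlation and kappa measure agreement, and two readers who both recognise the arm can agree closely while sharing the same bias. The report could then describe as blinded some readings that were not.

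**Working it through.** The plan gives no figure on this point, and the sample-size calculation does not bear on it. The check is to take each record in turn and ask whether the cast itself can show the arm and whether the stated masking hides it.

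| Record | En-masse arm | Two-step arm | Can the cast show the arm? | Is the arm hidden by the stated step? |
|---|---|---|---|---|
| Pre-intervention cast, timed as in the Clinical Procedure | Before any retraction | After canine retraction | Yes: the space is present in one arm only | No: only the name is covered |
| Pre-retraction cast, timed as in the Participant timeline | Before any retraction | Before any retraction | No reason that it should | Name-sealing may suffice |
| Interim monthly casts | Space closing in one step | Space left by the canines until full anterior retraction | Yes, once the canines have moved far enough | No: the sealing sentence does not name interim models, and a covered name would not hide the space |
| T1 cast or scan, seen alone | Space closed | Space closed | Need not | Name-sealing may suffice |

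**Site of the space.** The Rationale says only that there is a space. That it lies between lateral incisor and canine is an inference, from the canines moving back while the incisors stay. In en-masse treatment the front teeth move together, so by the same inference the remaining space lies behind the canine.

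**How many interim casts.** If retraction records begin only after canine retraction, as the Clinical Procedure implies, every two-step interim cast starts with the space present. If monthly models begin with canine retraction, the earliest may show little. The documents do not settle which applies, so no count or proportion can be given.

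**Which outcomes are reached.** Interim space and rate readings rest on the interim casts. Outcomes are defined as T0 to T1 differences, so any model-based difference that uses the late two-step cast as T0 is also affected. Anchorage loss is assigned to digital models in the outcome table and under Retraction records, but to CBCT in III) A]. It is exposed to the extent that the late cast, or a scan taken at the same stage, supplies its starting value.

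**Who reads.** II) D] gives the measuring to two blinded assessors. III) A] and III) C] give landmark identification, anchorage loss and data extraction to the principal investigator, who also allocates patients and takes the records (I) E]). II) D] itself says operators cannot be blinded.

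**The case against.** The strongest reply is that the blinded assessors may never see an interim cast. The sealing sentence covers pre and post records only, the sentence on interim models has the principal investigator as its subject, and outcomes are T0 to T1 differences. On that reading the interim casts expose no blinded reader. This stands as a real ambiguity. But the assessors are given the measurements of the study without exception, and if the principal investigator reads the interim casts, those readings are unblinded anyway. The two-step pre-intervention cast stays within the assessors' remit on either reading.

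A second reply is that visibility during treatment is inherent in comparing these techniques. That also stands: for interim readings the remedy is mainly to stop calling them blinded.

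Three stronger conclusions are tempting, and the documents do not support them:

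- A reader might infer that assessors cannot be blinded at all. At T1 the space is closed in both arms, so a final record seen alone need not show the group.
- A reader might infer that virtually every two-step interim cast is identifiable. Early in canine retraction the space may be small.
- A reader might infer a bias of material size in millimetres, from the cited study's roughly 1 mm of anchorage loss per 4 mm of incisor retraction and the 1 mm disagreement limit under Assessors Reliability. The ratio is one earlier study's result, not this trial's expectation. The limit concerns disagreement between readers, not a directional difference between arms, and sits alongside repeat readings, ICC and retraining.

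**Conclusion.** The point holds in limited form. Name-sealing does not hide the arm on the two-step pre-intervention cast as the Clinical Procedure times it, or on interim two-step casts once the canines have moved. The single-blind property therefore does not hold for interim space or rate readings, or for T0 to T1 readings that use that late cast. It can hold for T1 records read alone, and for T0 records taken before any retraction.

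The extent is stated as which readings are affected; no bias in millimetres or months can be derived. The conclusion assumes that the space is visible on a cast, which the Rationale's remark on appearance supports, and that its site is as inferred. Duration, the primary outcome, also relies on visit records, and no blinded person is named to judge closure. The documents do not show that unmasked casts would change the duration result, and masking casts alone would not blind it.

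**What to change.** 1. Reconcile the Clinical Procedure with the Outcomes section and Participant timeline, so that T0 records in both arms are taken before any tooth is retracted.
2. Reconcile II) D] with III) A] and III) C], so that the two assessors rather than the unblinded principal investigator read anchorage loss from the T0 and T1 records. State whether those are models or CBCT.
3. Give the T0 and T1 files random codes with no visit date, and mask the canine-incisor region where the landmarks allow. The reference planes are not defined, so how much can be hidden must be checked first. Present the files in random order across patients and time points, and lock the readings before the assessors open any interim model.
4. Restate II) D] so that blinding is claimed only for these T0 and T1 measurements. Declare interim space and rate readings, and the judgement of closure, unblinded.

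The models are already to be digitised, so the third step costs file preparation and the fourth costs wording. The first may add one impression in the two-step arm if none is now taken before canine retraction. Without the first two steps, masking achieves little. The price is a more modest blinding claim.

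### Two blinded assessors are planned, but no rule brings both readings into the analysis; reconcile who measures and analyse the mean of the two readings

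*Combined protocol and SAP*

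**What the plan says.** **Who measures.** Section II) D] Blinding makes the outcome assessors the only blinded party and, after patient names are concealed on the pre and post radiographs and study models, says: "Then two assessors will carry out, blindly and independently, the measurements and analysis of the study". The monthly interim models are not named separately.

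Section III) A] Data collection methods gives the work to one person: "Anchorage loss: will be accessed by the principal investigator via CBCT taken before and after the completion of retraction". It also has the principal investigator digitize the models and identify the landmarks. Section III) C] Statistical Analysis adds: "The principle investigator will be responsible for the extraction of the required data from the CBCT taken before and after retraction", together with the study models, before the data go to the statistician.

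**What the paired readings are for.** Under Assessors Reliability:
- Both examiners measure a model (how many is not stated) on two occasions a week apart, as the basis for agreement within and between them.
- On discrepancies, the plan says: "The supervisor will compare the measurements of the two assessors for disagreement with a difference of more than one millimeter".
- The spread of readings is then used to judge how well each assessor performs.
- The less reliable examiner is to be retrained and replaced. An ICC and a kappa are to be calculated, with the benchmark "ICC values between 0.7 and 0.9 represent good reliability".

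**What is analysed.** Section I) D] Outcomes defines outcomes as the difference between T0 (start of retraction) and T1 (complete space closure). No section says whether the two assessors' readings are combined, which one is used, or what follows a flagged disagreement.

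**The concern.** If two independent blinded readings exist, using one of them gives up precision that the other could supply. It also leaves the analysed value undefined. With no rule fixed in advance, the plan does not exclude a choice between readings after both are known. The only described route to the statistician runs through the principal investigator. That person takes the records and allocates patients (section I) E] Participant timeline), and so appears to overlap with the operator whom section II) D] declares unblinded.

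The disagreement limit is wide for the quantity measured. A comparison cited in the literature review reports about 1 mm of molar anchorage loss for 4 mm of incisor retraction. Two readers could differ by that whole 1 mm without being flagged.

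At stake is the precision, and the protection from observer bias, of the millimetre and degree outcomes in at most 30 patients (15 per group).

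**Working it through.** **Inputs**
- Two independent blinded readers (section II) D]).
- Single-reading ICC *r* of 0.7 to 0.9 (Assessors Reliability). This is a quoted benchmark for good reliability, neither observed nor stated as an acceptance limit. It is treated as the ICC of one reading at one time point, since the reliability exercise is on a model.
- Outcomes are T0–T1 differences (section I) D]).
- Assumptions not in the documents: equal precision and independent errors for the two readers, and a true T0–T1 correlation *c*, shown at 0, 0.5 and 0.8.

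**Step 1. The plan's sample size, for context.** Section I) F] uses SD 0.76, difference 1.0, alpha 0.05 (two-sided assumed) and power 0.8. The formula 2 × (1.960 + 0.842)² × 0.76² / 1.0² gives 9.07, so 10 per group, as stated. A t-based calculation gives 11. No unit or outcome is given for the 0.76, so it cannot be tied to a model or CBCT reading.

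**Step 2. One time point.** The mean of two readings has reliability 2r/(1+r):
- r = 0.7: 1.4/1.7 = 0.824
- r = 0.9: 1.8/1.9 = 0.947

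Error variance halves, and total variance is multiplied by (1+r)/2, that is 0.85 or 0.95. The equivalent gain in patients is 1/0.85 = 1.18 or 1/0.95 = 1.05.

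**Step 3. Change from T0 to T1.** Set the variance of one reading to 1. The true change has variance 2r(1−c). Error adds 2(1−r) with one reader and (1−r) with the mean of two. The variance of a group difference scales as variance/n, so the ratio of the two totals is the equivalent increase in patients.

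| c | r | One reader | Mean of two | Ratio |
|---|---|---|---|---|
| 0 | 0.7 | 1.40 + 0.60 = 2.00 | 1.40 + 0.30 = 1.70 | 1.18 |
| 0 | 0.9 | 1.80 + 0.20 = 2.00 | 1.80 + 0.10 = 1.90 | 1.05 |
| 0.5 | 0.7 | 0.70 + 0.60 = 1.30 | 0.70 + 0.30 = 1.00 | 1.30 |
| 0.5 | 0.9 | 0.90 + 0.20 = 1.10 | 0.90 + 0.10 = 1.00 | 1.10 |
| 0.8 | 0.7 | 0.28 + 0.60 = 0.88 | 0.28 + 0.30 = 0.58 | 1.52 |
| 0.8 | 0.9 | 0.36 + 0.20 = 0.56 | 0.36 + 0.10 = 0.46 | 1.22 |

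Better readers gain less: at r = 0.95 and c = 0.5 the totals are 1.05 and 1.00, a 5% gain.

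**Step 4. Power, as illustration only.** Suppose 0.76 were the SD of an analysed single reading in millimetres and *r* applied to it directly. Averaging would reduce the SD to 0.76 × √0.85 = 0.701 or 0.76 × √0.95 = 0.741. T-based power at 15 per group would move from 0.935 to 0.965 or 0.946. If 0.76 is a duration, this does not apply.

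**Step 5. Which outcomes benefit.** Duration comes from visit records and monthly models at 4-weekly visits. Reading error reaches it only through the judgement that the space is closed. Pain is patient-reported. What remains is anchorage loss, anterior tooth position and rate of retraction.

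**The case against.** The strongest reply is that the plan may not contain two full sets of readings. It says that two assessors carry out the measurements, but the reliability exercise refers to a model, with no number given, and other sections give landmarking, anchorage loss and data extraction to the principal investigator. On that reading, the second assessor exists for quality control and the more basic defect is the contradiction over who measures, which averaging alone does not settle. This stands, and the fix must begin there.

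A reader might infer three stronger things that the documents do not support:
- That every record is read twice. No section says so.
- That the plan discards one reading, or uses it only to grade the assessors. The plan is silent on which value is analysed; silence is not a decision to drop a reading, and no section describes choosing one after both are seen.
- That averaging is free. This would hold only if both assessors already read all the records and no pair needed re-reading.

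The size is also uncertain. The correlation has no source in the documents, and 0.8 is not a ceiling: at 0.9 the same formula gives 68% and 36%. Training and an experienced examiner, both planned, could put the ICC above the benchmark range and shrink the gain. An equal-weight mean beats the better reader only if the other's error variance is less than three times as large, and it does not remove a bias that both readers share.

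None of this supplies the missing rule.

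**Conclusion.** The point holds as an unspecified analysis rule together with a contradiction over who measures. Two blinded independent readings are planned, their stated uses are confined to reliability and an unresolved 1 mm flag, and the analysed data are described as coming from the principal investigator. Analysing the mean of the blinded pair is more precise and less open to bias.

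The gain, for ICC 0.7 / 0.9, is equivalent to 18% / 5% more patients at a true T0–T1 correlation of 0, 30% / 10% at 0.5, and 52% / 22% at 0.8. These figures rest on equal reader precision, independent errors, a quoted ICC benchmark and an assumed correlation. They should be given as a range and confined to anchorage loss, tooth position and rate of retraction. A reader might take the larger figures as a gain in power for the trial's main question; the documents do not support that, because the primary outcome is a duration. This is a worthwhile refinement that does not threaten the primary comparison.

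**What to change.** First, reconcile section II) D] with sections III) A] and III) C], so that the analysed model and CBCT measurements come from the two blinded assessors and the principal investigator's part is limited to collecting and passing on records.

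Then add under Assessors Reliability, with a cross-reference in III) C]:

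> Both assessors read all T0 and T1 models and CBCT records blind and independently. The analysed value at T0 and T1, and at interim visits where both read, is the mean of their two readings. Where readings differ by more than 1 mm, or by more than a prespecified limit for measurements in degrees, both assessors re-read blind and the mean of the re-readings is used. The ICC is calculated on the readings made before any re-reading.

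The limit in degrees has to be set, since the plan has none. The text should also state whose readings enter the mean if an examiner is replaced, and whether the monthly models are double-read.

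No new staff are needed. The cost is a short text change and some re-reading, plus additional reading work if double reading was intended only for a subset of records.
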